1. Hypothesis and Specific Aims

Overarching Hypothesis: Insulin signaling is a critical neurobiological substrate of anhedonia in mood disorders

Specific Hypotheses: In individuals with mood disorders, objective and self-reported measures of anhedonia and reward behaviors are associated with alterations in insulin signaling-related molecular, cellular and neural substrates. Considering the role of insulin in the regulation of energy expenditure, we primarily hypothesize that individuals with mood disorders will display decreased willingness to make effort for rewards, relative to healthy controls; and that this abnormality will be associated with:

- a) Molecular: Differential gene and protein expression of the metabolic (i.e. PI3K/Akt) and mitogenic (i.e. Ras/MAP kinase) components of the insulin signaling pathway, as well as with components of reward-related processes (i.e. dopamine receptors and transporter)
- b) Physiology: Reduced peripheral sensitivity to insulin and corresponding metabolic correlates, including increased body mass index and dyslipidemia (i.e. peripheral insulin resistance)
- c) Neural Circuits: Diminished response to insulin in cortico-striatal networks (i.e. brain insulin resistance)

Overarching Aim: To determine the role of insulin signaling on the neurobiological substrates subserving anhedonia within individuals with mood disorders.

Specific Aims:

- a) Molecular: Assessment of components of the insulin cascade, as well as of anhedonia and reward-related processes, using a proteomics and gene expression approach;
- b) Physiology: Measurement of peripheral sensitivity to insulin and metabolic correlates, including body mass index and dyslipidemia;
- c) Neural Circuits: Evaluation of the insulin sensitivity of prefrontal (e.g. prefrontal cortex) and striatal (e.g. nucleus accumbens, ventral tegmental area) networks in the resting-state and during an effort-based decision making test, using acutely administered intranasal insulin and functional magnetic resonance imaging (fMRI);
- d) Behavioral: Measurement of willingness to make effort for rewards, as well as of other components of reward response and anhedonia, using validated behavioral tasks and clinical scales (e.g. Snaith-Hamilton Pleasure Scale SHPS).

2. Background and Rationale

Mood disorders (i.e. major depressive disorder [MDD] and bipolar disorder [BD]) and metabolic disorders (i.e. type 2 diabetes mellitus [T2DM], obesity) are highly prevalent and impactful conditions. Epidemiological studies have identified depressive disorders and diabetes as leading causes of disability worldwide¹. Mood and metabolic disorders are also major causes of excessive and premature mortality. Mortality studies indicate that with individuals with MDD or BD have markedly reduced life expectation, on average of 10-15 years²; the main driver of excess and premature mortality in this population is cardiovascular disease and/or diabetes complications^{2,3}. Conversely, depressive symptoms, particularly anhedonia, are consistently reported in T2DM populations and have been associated with an increased incidence of complications and all-cause mortality^{4,5}.

Comorbid metabolic disorders are extremely common in individuals with mood disorders. Metaanalytic studies have documented that individuals with MDD or BD have an approximately 2-fold increased risk of T2DM, relative to the general population⁶. It is estimated that the prevalence of Project Title: Anhedonia and the insulin pathway: a mechanistic nexus for the mood and metabolic disorders comorbidity

T2DM in individuals with mood disorders is between 8 and 10%, whereas the prevalence of metabolic syndrome is approximately 30%⁷. Convergent lines of inquiry indicate that mood and metabolic disorders have a bidirectional association⁸⁻¹⁰. For example, it is reported that individuals with T2DM have an approximate 2-3 fold greater risk for subsequently declaring MDD or BD¹¹. Nonetheless, the association between metabolic and mood disorders is still poorly understood. Overlapping risk factors (e.g. diet, physical activity, psychotropic medications, sleep, childhood trauma) have an important role⁶; however there is insufficient data on the extent to which these environmental factors are responsible for the mood-metabolic disorders comorbidity. Mechanistic studies have documented a role for the biological substrates of metabolic and mental disorders, such as neurostructural alterations ^{12,13}, and differences in peripheral biomarkers¹⁴. A recent genetic study identified multiple genes that are likely shared between mood and metabolic disorders; pathway analysis revealed an over-representation of genes that encode for molecules involved in dopamine signaling¹⁵. There is considerable evidence that dopamine has a core role in anhedonia and reward-related behaviors, indicating that this is a particularly promising area for further advancing the knowledge on the association of mood and metabolic disorders.

1.1. Mood Disorders and Anhedonia

Anhedonia is defined as markedly diminished interests or pleasure in all, or almost all, activities most of the day, nearly every day for an extended period of time. Anhedonia is a core criterion item for the diagnosis of a major depressive episode. Anhedonia is also a robust predictor of poorer longitudinal course of symptoms of MDD and BD¹⁶⁻¹⁹. Existing psychological and pharmacological treatments are relatively ineffective for treating anhedonia, as standard medication treatments have little effect and in some cases may even worsen anhedonic symptoms^{17,20}. As a result, anhedonia has been described as one of the most prevalent residual disturbances following treatment with selective serotonin re-uptake inhibitors^{17,21,22}.

Anhedonia includes elements of multiple reward processes²³⁻²⁵. Reward systems are primarily responsible for responses to positive motivational situations or contexts, such as reward seeking, and reward/habit learning²³⁻²⁵. Reward is a broad and heterogeneous construct. To effectively study it, it is important to consider its three main subconstructs: (1) reward responsiveness, including anticipatory and initial hedonic responses; (2) learning, or the acquisition of information about stimuli, actions and context; and (3) valuation, including the measurement of value and/or incentive salience of a prospective outcome and the willingness to work for it (i.e. effort)^{26,27}.

Evidence indicates that individuals with mood disorders exhibit abnormalities in multiple of these reward subcomponents²⁸⁻³². Anhedonia is closely related to reward anticipation, motivation and decision making^{29,33}. A consistent finding has been a decrease in the willingness to expend effort and/or in the modulation of effort expenditure for rewards^{28-31,33}. It has been demonstrated that individuals with depression display reduced motivation on effort-based decision making²⁹⁻³¹, a dissociation between liking a reward and the willingness to exert effort for it²⁸, an increased subjective feeling of having exerted more effort³¹ and a lower ability to effectively use information about rewards to modify their behavioral choices²⁹.

1.2. Neural Substrates of Anhedonia and Reward

The most well-characterized reward circuit is the mesolimbic pathway, which consists of dopaminergic projections from the ventral tegmental area (VTA) to the nucleus accumbens (NAc)^{34,35}. These areas are heavily interconnected with the prefrontal cortex (PFC), amygdala and hippocampus, among other areas³⁴. Specifically, connections between the dorsolateral PFC (dlPFC), NAc and VTA

have a key role in motivated behavior³⁶. Indeed, connectivity between the PFC and striatal areas during reward-related tasks negatively correlates with anhedonia in individuals with MDD^{37,38}.

Dopaminergic neurotransmission has been highlighted as a key component of multiple reward processes³⁹. Dopamine signaling has traditionally been implicated in arousal, motivation and psychomotor activation (i.e. incentive salience models), and reward learning/reinforcement (i.e. prediction error models)⁴⁰⁻⁴². Recent work proposes that dopamine signals value, or the available reward for a certain effort, which is then employed for both learning and motivational functions⁴². Multiple studies from different lines of research, such as genetics, neuroimaging and pharmacology, have documented abnormalities in dopaminergic neurotransmission in individuals with mood disorders (8, 9). For example, neuroimaging studies have demonstrated alterations in dopamine receptor and transporter binding in individuals with MDD⁴³⁻⁴⁵. Conversely, the Val(158)Met polymorphism of the catechol-O-methyltransferase (COMT) gene, which affects dopamine catabolism and modulates prefrontal dopamine levels, has been associated with measures of anhedonia^{46,47}. Overall, abnormalities in reward-related behaviors and dopaminergic transmission are well-established features of mood disorders phenomenology and neurobiology.

1.3. Brain Insulin Signaling Pathway, Dopamine Signaling and Reward

Dopamine signaling within and across brain circuits is in interplay with many systems relevant to reward, including the insulin signaling pathway^{34,48,49}. Insulin acts via the insulin receptor (INSR). Activation of INSR initiates the recruitment of the insulin receptor substrate (IRS) family of proteins, which organize and mediate signaling cascades^{50,51}. IRS1 and IRS2 are the most extensively studied substrates; they are expressed in the brain and have well-documented effects on insulin signaling and glucose homeostasis⁵²⁻⁵⁴. Insulin binding to INSRs activates several divergent signaling pathways, including the metabolic pathway (i.e. PI3K/Akt), which affects glucose and lipids homeostasis; and the mitogenic pathway (i.e. Ras/MAP kinase), which is implicated in the regulation of apoptosis and cell proliferation/differentiation.

Multiple brain regions that are relevant to reward systems have relatively increased expression of INSRs (e.g., PFC, hippocampus, amygdala, substantia nigra)^{22,23}. Specifically, midbrain dopamine neurons widely express INSRs⁴⁹. Imaging studies have reported that, in healthy individuals, insulin modulates brain activity in the hypothalamus, hippocampus and prefrontal cortex³⁴⁻³⁶. Brain insulin signaling has traditionally been implicated in glucose and lipid metabolism, and eating behavior. However, replicated evidence, from multiple studies, has documented that insulin also has a role on emotional processing⁵⁵⁻⁵⁷ and reward processes, including, but not limited to, those pertaining feeding behaviors and energy expenditure^{58,59}.

An important way insulin affect reward processes is via interaction with dopaminergic signaling. Evidence indicated that insulin modulates multiple components of dopamine transmission, including synthesis and transport, receptors function and reuptake and degradation. For example, lower expression and function of tyrosine hydroxylase (TH), the rate-limiting enzyme in dopamine biosynthesis, have been reported in animal models of diabetes^{60,61}. In humans, insulin resistance was associated with less endogenous dopamine at D2/3 receptors in the ventral striatum and NAc, in both obese and non-obese participants^{62,63}. A separate study documented that weight loss following bariatric surgery was associated with an increase in D2 receptor availability⁶⁴.

Termination of dopamine action, which is via reuptake from the synaptic cleft by the dopamine transporter (DAT), or by degradation by monoamine oxidases (MAOs) A/B and COMT, has also been shown to be affected by insulin. Studies with animal models of diabetes have reported lower availability and activity of DAT^{65,66} and lower activity of COMT⁶⁷; whereas a murine model with a

brain specific knockout of the insulin receptor reported that decreased insulin function in the brain resulted in increased expression of MAO A/B in the striatum and NAc⁶⁸. As a result, evidence indicates that insulin sensitivity modulates reward behavior in obese adults, wherein insulin resistance was associated with a stronger preference for immediately receiving a smaller, but certain, monetary reward over delaying the receipt of a larger, but less certain one (i.e. greater delay discounting)⁶⁹.

1.4. Insulin Signaling, Anhedonia and Major Depressive Disorder

The epidemiological, phenomenological and biological associations between mood disorders and metabolic disturbances have been amply documented. The foregoing observations provide the rationale for hypothesizing that there is a neurobiological association between metabolic disorders (e.g. diabetes) and mood disorders. The devastating impact of mood and metabolic disorders on affected individuals underscores the importance of urgently understanding better the basis of this association. Anhedonia is a well-described symptom that similarly occurs in both disorders. The extant evidence of the association between insulin and dopamine signaling and the potential repercussions of disturbances in this system indicates that this is a promising target for clinical and neurobiological investigations. The interface between anhedonia and insulin represents a unique opportunity to integrate innovative and transdisciplinary lines of research in an investigative platform aiming at providing a more accurate and refined assessment of relevant mechanisms in the mood-metabolic disorders comorbidity.

2. Preliminary Data

Using the "Gene Expression in Postmortem DLPFC and Hippocampus from Schizophrenia and Mood Disorders" (dbGaP accession number phs000979.v1.p1) database, which contains microarray data from the post-mortem dlPFC (healthy controls [HC]: n = 209; patients: n = 321) and hippocampus (HC: n = 180; patients: n = 196), we conducted a hypothesis-driven analysis through the a priori selection of 12 dopamine- and 3 insulin-related genes (manuscript under review). Results showed that, in the dlPFC, after adjustment for relevant covariates, expressions of insulin receptors- (i.e. INSR, IRS1/2) and dopamine regulation-related genes (e.g. TH, DRD1-5, DAT) were influenced by body mass index (BMI), with significantly lower expression in high BMI patients with mood or psychotic disorders (Figure 1). In the hippocampus, we observed significantly lower expressions of these genes, which were not affected by BMI.

Genes that were differentially expressed between groups were selected for mediation analyses. Diagnosis by BMI effects on expression of dopamine genes were fully mediated by expression of INSR. Analysis of conditional indirect effects showed interactions between INSR and BMI, indicating significantly stronger indirect effects at higher BMI values. In the hippocampus, we observed that expression of insulin receptor substrate 1 and 2 fully mediated the effects of diagnosis on expression of dopamine genes (Figure 2). All models were significant (e.g. DRD1: $R^2 = 0.31$, $F_{6,385} = 29.519$, p < 0.001). These results suggest that the differential expression of dopamine-related molecules in the postmortem brain of individuals with mental disorders is related to altered expression of insulin signaling genes. We also observed that obesity has region-specific moderating effects on gene expression and co-expression, supporting the hypothesis that metabolic systems are critical mediators of dopaminergic function and providing the rationale for further investigation.

Figure 1 – Mean standardized expression values of insulin and dopamine signaling genes in the dorsolateral prefrontal cortex, according to group (HC vs. MI) and obesity (BMI \geq 30 kg/m²). HC: healthy controls; MI: mental illness; BMI: body mass index.

[figure not shown]
[figure not shown]

Figure 2 – Unstandardized path coefficients for a mediation model in the hippocampus, adjusted for age, gender, race, ethanol and nicotine/cotinine. * p < 0.05; ** p < 0.001.

[name] Research Proposal Project Title: Anhedonia and the insulin pathway: a mechanistic nexus for the mood and metabolic disorders comorbidity

3. Design and Methodology

Study population: We propose to recruit 50 adults between the ages of 18 to 50 years: 25 patients with DSM-5 defined MDD or BDI/II, in a depressive episode, recruited from the Mood Disorder Psychopharmacology Unit, University Health Network, and 25 age- and sex-matched healthy controls recruited through local advertisements in the community.

Inclusion criteria (patients):

- 1. Age 18-50
- 2. DSM-5 defined MDD/BD and a total score ≥20 on the Montgomery-Åsberg Depression Rating Scale (MADRS) and no history of dementia or intellectual disability
- 3. A written, voluntary informed consent prior to study enrollment

Exclusion criteria (patients):

- 1. Use of insulin and/or oral hypoglycemiants, due to its confounding effects
- 2. Diagnosis of possible or probable AD, MCI, or any other dementia
- 3. History of neurological disorder, or evidence of neurologic or other physical illness that could produce cognitive deterioration
- 4. Substance use disorder within 3 months before screening or a positive baseline toxicology screen
- 5. Presence of clinically unstable general medical illness
- 6. Pregnancy or breastfeeding
- 7. MRI contraindications

Inclusion criteria (healthy controls):

- 1. Age 18-50
- 2. A written, voluntary informed consent prior to study enrollment

Exclusion criteria (healthy controls):

- 1. Use of insulin and/or oral hypoglycemiants, due to its confounding effects
- 2. Presence of any current or lifetime psychiatric or neurological conditions
- 3. Substance use disorder within 3 months before screening or a positive baseline toxicology screen
- 4. Presence of clinically unstable general medical illness
- 5. Pregnancy or breastfeeding
- 6. MRI contraindications

Study Procedures: Single-dose, randomized, controlled, double-blinded, cross-over study (50 participants)

Screening and Baseline Assessment: Patients and healthy controls will first meet, in-person or virtually, with a staff psychiatrist for a clinical consultation or a research team member, respectively. After obtaining consent and if inclusion criteria are met, a medical comorbidity questionnaire will be administered to screen for concurrent and lifetime medical conditions. Participant's demographic characteristics and current medications, as well as lifetime psychotropic medications received will be recorded. We will also assess dietary intake with the Diet History Questionnaire III (DHQ III); smoking, by questioning number of cigarettes smoked per day, age when smoking started, and quitting date, if applicable, to calculate a smoking pack-year history; physical activity using the International Physical Activity Questionnaire (IPAQ); and alcohol and/or substance abuse. In addition, we will assess demographics, socioeconomic status, medical history, and family psychiatric history; childhood trauma history with the Childhood Trauma Questionnaire (CTQ) will also be assessed. Participants will also be asked to complete an MRI screening questionnaire to ensure that they have no contraindications. The following self-reported measures will be carried out: Perceived Deficits Questionnaire-Depression (PDQ-D), Sheehan Disability Scale (SDS), UCLA life Stress (Episodic), DeJong Gierveld Loneliness Scale, and Pittsburg Sleep Quality Index (PSQI) (Table 1).

When in-person visits are possible, participants will complete a urine drug screen. Female participants will be asked to do blood work to confirm they are not pregnant.

Physiological Assessment: Anthropometric (i.e. BMI, waist-hip ratio) and metabolic measurements (i.e. fasting glucose, fasting insulin, glycated hemoglobin, lipids and HOMA-IR) will be completed at each study visit (1-3). In addition, physical activity and energy expenditure will be measured using an accelerometer. Participants must wear the accelerometer at all times for one week and return it upon Visit 3 for data collection and analysis. Additionally, a heart rate monitor device will be connected to the accelerometer that will monitor heart rate variability over one day of the week that the subjects wear the accelerometer.

Laboratory Assessment:

Routine: the following laboratory tests will be completed:

Triglycerides
Total Cholesterol
Insulin
Glucose
HbA1c
C-Peptide
IGF-1
TSH
Free T4
Free T3
C-Reactive Protein
hCG

Biomarkers: High sensitivity CRP and TNF α will be measured at both visits (hs-CRP only). Ultrasensitive ELISA will be used to measure high-sensitivity CRP and TNF- α , TNF-RI and TNF-R2 (measured at both visits). For exploratory mechanistic analysis, a 10-plex immunoassay of

inflammatory cytokines will be measured at both visits (e.g. IFN- γ , IL-1 β , IL-2, IL-4, IL-6, IL-8, IL-10, IL-12p70, IL-13). Blood will be collected after a 12 hour fast and centrifuged at 1000g for 15 min at 4°C; plasma will be stored at -80 °C.

Behavioral assessment: These tasks are simple, user-friendly tools that provide an opportunity, when used in conjunction with the most widely used questionnaires, to gain novel insights on reward behaviors in mood disorders.

- a) The primary behavioral measurement will be effort-based decision-making, assessed using the Effort-Expenditure for Rewards Task (EEfRT)³³, which will be done in a fMRI paradigm⁷³, as described below during Visits 2 and 3.
- b) Assessments will include the validated anhedonia scale Snaith-Hamilton Pleasure Scale (SHPS), the mood questionnaires Montgomery-Åsberg Depression Rating Scale (MADRS) and Young Mania Rating Scale (YMRS) during each study visit, and the Bandit Task during the first visit.

Neural Circuits Assessment: A promising tool to study the effect of insulin on CNS is intranasal insulin, which is delivered directly into the brain, without relevant effects on peripheral glucose^{76,77}. A single dose of intranasal insulin has been shown to influence brain activation, increasing regional perfusion and functional connectivity between the hippocampus and the PFC⁷⁸⁻⁸⁰. Acute administration of intranasal in randomized, placebo-controlled, cross-over designs has been previously used to determine regional responses to insulin in the resting-state or during tasks^{78,80}.

After screening and baseline assessment, participants will receive a crossover treatment assignment of either insulin or diluent followed by an MRI scan, with a washout period of 1 week. Therefore, participants will receive a total of 2 MRI scans throughout the course of the study- one following the first treatment, and one following the second treatment. The subsample will be enriched for the presence of self-reported anhedonia, using a score of greater than 2 on the SHPS as a cut-off, which provides the best discrimination between "normal" and "abnormal" level of hedonic tone⁸¹. This subsample will also have equal representation of normal weight and obese participants.

To proxy insulin activity within pre-selected brain regions, we will use a provocation paradigm, involving the administration of exogenous intranasal insulin, based on the published work of other research groups research groups Activation of brain regions will be assessed during the resting state and task-based reward paradigm (i.e. EEfRT), following an intranasal administration of either 160 units of intranasal insulin or diluent (insulin and placebo will be prepared as nasal sprays), in a randomized, double-blinded, cross-over design. Please refer to the pharmacy manual for randomization details. A hypothesis-driven region of interest approach will be used to investigate initially the striatum and the medial PFC (mPFC). Willingness to make effort for rewards will be measured with the EEfRT³³. Briefly, participants have to select between an easy and a hard task. Both tasks involve pressing a key for a predetermined amount of time. The hard task offers more money (variable amounts), but is harder and takes twice as long. Participants make their selection knowingly under different win probabilities (i.e. they might not win money even if they are successful if the win probabilities are low). This task will measure proportions of hard-task choices with varying probabilities of reward and reward magnitudes. To provide stable estimations, the fMRI task will be conducted in three runs⁷³.

Table 1

Assessment	Baseline (V1)	First Spray (V2)	Second Spray (V3)		
General Information					
Demographics	✓				
Questionnaire					
Medical Comorbidity	✓				
Questionnaire					
Family Psychiatric	✓				
History					
Questionnaire	,				
SES Questionnaire	√				
MRI Questionnaire	✓	✓	✓		
Anthropometric Measures					
Height (ft)	✓				
Weight (kg)	✓	✓	✓		
Blood Pressure	✓	✓	✓		
(mmHg)					
Heart Rate (bpm)	✓	✓	✓		
Waist/hip	✓				
Circumference (cm)					
Physical Activity/	✓	✓	✓		
Energy Expenditure/					
7-Day Accelerometer					
Wear Time Log					
Laboratory Assessme					
Triglycerides	√	√	√		
Total Cholesterol	√	√	√		
Insulin	√	√	√		
Glucose	✓	✓	✓		
HbA1c	✓	✓	✓		
C-Peptide	✓	✓	✓		
IGF-1	✓	✓	✓		
TSH	✓	✓	✓		
Free T4	✓	✓	✓		
Free T3	✓	✓	✓		
C-Reactive Protein	✓	✓	✓		
hCG	✓				
Imaging					
fMRI-EEfRT		✓	✓		
Dimensional Measures					
Clinician Administered					
YMRS	✓	✓	✓		
MADRS	✓	✓	✓		
Bandit Task	✓				
Self-Report					

SHPS	✓	✓	✓	
PDQ-D	✓			
SDS	✓			
UCLA Life Stress	✓			
Interview (Episodic)				
CTQ	✓			
DeJong Gierveld	✓			
Loneliness Scale				
Diet History	✓			
Questionnaire (III)				
IPAQ	✓			
PSQI	✓			
Neurocognitive Tasks				
DSST	√	 	√	
RAVLT	✓	✓	✓	
TMT A/B	✓	✓	✓	

Project Title: Anhedonia and the insulin pathway: a mechanistic nexus for the mood and metabolic disorders comorbidity

Imaging procedures will be started with a safety monitoring for glucose and cardiovascular vital signs. An insulin/placebo spray will be administered intranasally and, within 30 min, fMRI measurement will be performed. Venous blood samples, for determination of plasma glucose and insulin concentrations, will be obtained at the time of the insulin/placebo spray administration and immediately after the scan. The 2 scans for each individuals will be acquired on the same scanner. Subjects will be scanned using a 3.0-Tesla Signa HDx scanner with an 8-channel phased-array receiver coil (GE Healthcare, Milwaukee, Wisconsin) consisting of a structural and functional neuroimaging, comprising:

- Whole-brain 3-D T1-weighted Inversion-Recovery prepared Fast Spoiled Gradient-Echo (IRi. FSPGR) anatomical scan with the following parameters: (TI/TR/TE = 450/8/3 ms, matrix size 256 \times 256, field of view 22 \times 22 cm, slice thickness = 1 mm, and flip angle = 15°)
- Whole-brain, T2*-weighted BOLD echo planar imaging (EPI) during awake resting state with the ii. following parameters: (TR/TE = 2000/30 ms, 3.5 x 3.5 x 3.5 mm voxel size, field of view 24x24 cm, 39 slices, slice thickness 3.5 mm, matrix size 64x64, number of frames = 405, flip angle =
- Three runs of whole-brain, T2*-weighted BOLD EPI series during task-based reward paradigm iii. with the same parameters as in ii.

4. Study Treatment

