Potential Challenges and Ways to Overcome Them: The primary challenge in this study is that of recruiting and retaining 150 participants over a 3-year period. Given the experience and volume of the mood disorders clinics involved in this study, we believe that this goal is attainable. There are two potential limitations in our sample composition proposal. First, it is expected that the majority of participants recruited in tertiary mood disorders clinics will report clinically significant anhedonic symptoms. Nonetheless, it is possible that some of the subconstructs analyzed will not display satisfactory psychometric properties for contrast/comparisons. Second, we propose to pre-stratify our sample based on overweight/obesity. There is a well-documented association between adiposity and insulin sensitivity; though these are not perfectly collinear constructs. There are no, however, validated, publicly available, normative data of anhedonic symptoms, whereas gold-standard evaluations of insulin sensitivity are invasive and costly (e.g. hyperinsulinemic euglycemic clamp); therefore approximations are initially necessary. We propose to conduct a preliminary analyses after one third of the sample (n=50) is recruited and reevaluate the sample selection procedures.

A key challenge for the interpretation of results will be how to account for the role of potential confounding factors. These factors include, but are not limited to, psychotropic medications, smoking, socio-demographic characteristics, dietary and lifestyle factors. We opted for a "real-life" naturalistic treatment-seeking sample, as we seek to recruit a sample that is representative of other clinical samples. Moreover, ethical considerations preclude us from withdrawing or deferring initiation of medications. Therefore, we propose to systematically measure these confounding factors and use it as control and/or sub-stratification variables, as appropriate.

ADVERSE EVENTS

Definitions

Adverse event

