We expect that results from this study will advance the knowledge on the mechanistic basis of anhedonia, which is a critical step for the development of targeted and more effective therapeutic options for individuals with MDD and BD. In addition, by highlighting the role of insulin signaling in the pathophysiology of mood disorders, we hope to refine the conceptual framework on the association between mood and metabolic disorders. Understanding better the impact of insulin signaling disturbances has tremendous potential to reframe how researchers and clinicians conceptualize mood disorders. Ultimately, the aim is to support the development of empirically supported, integrated therapies, such as medications and/or behavioral modifications (e.g. exercise programs) that target both mood and metabolic manifestations. These are urgently necessary to address adequately the multifaceted needs of affected individuals and families.

Future research plans consists of eventually establishing a longitudinal cohort, focused on the interface of metabolic and mood disorders. There is a clear need for longitudinal studies in this area; it is the only design that allows for the exploration of developmental trajectories and for definitive conclusions on causality. Moreover, our research team has ongoing collaborations with international groups, including Brazil, China, Denmark and South Korea, which have generated published articles and collaborative projects; we also intend to further develop these collaborations and explore opportunities for replication studies and cross-cultural comparisons. Finally, our research group has extensive experience with clinical trials, especially with metabolic/inflammatory treatments, such as the immunomodulatory infliximab and the antidiabetic medication liraglutide. We expect that this study will provide opportunities for translational studies, specifically by identifying novel pharmacological targets and/or subgroups of individuals (e.g. obese patients with disturbances in reward valuation) more likely to respond to novel therapies.

References

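### The glucose-lowering drug exclusion stops at insulin and oral agents, so users of other such drugs can enter although the stated reason, confounding, applies to them too

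*Combined protocol and SAP*

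**What the plan says.** Section 3 (Design and Methodology) lists the same drug exclusion for patients and for healthy controls: "Use of insulin and/or oral hypoglycemiants, due to its confounding effects". The nearest other medical exclusion, also in both lists, is "Presence of clinically unstable general medical illness". Neither list excludes diabetes, treatment for obesity, or glucose-lowering drugs as a class.

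The same section sets the sample at 25 patients and 25 controls: "We propose to recruit 50 adults between the ages of 18 to 50 years". Under Neural Circuits Assessment it adds: "This subsample will also have equal representation of normal weight and obese participants". Under Physiological Assessment, the metabolic measures taken at each of visits 1 to 3 are "fasting glucose, fasting insulin, glycated hemoglobin, lipids and HOMA-IR".

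Section 6 makes insulin signaling and dopamine metabolism the mediator between mood disorder and reward behavior. It offers obesity and medications as example moderators, to be used if appropriate. Covariates are left open, with smoking and psychotropic drugs singled out for special attention. Section 3 has current medications recorded at baseline.

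**The concern.** The exclusion gives its own purpose: to keep treatment-related confounding out of a study about insulin. That purpose turns on a drug's action, while the wording sorts drugs by type and route. Followed literally, the rule admits people it was meant to keep out, in either group.

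The exposed quantities matter to the study. Fasting insulin, glucose, HbA1c and HOMA-IR are its peripheral measures of insulin sensitivity, and insulin signaling is the mediator. The background in section 1.3 also links insulin resistance in obese adults to altered reward choices. On the protocol's own reasoning, a drug that changes insulin sensitivity could therefore affect both mediator and outcome. If use differed between patients and controls, part of a group difference in these measures, or part of an estimated indirect effect, would reflect treatment and not mood disorder.

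**Working it through.** **Text check.** The plan states no figure on this point, so there is none to reproduce. The question is whether any rule catches a person stable on a glucose-lowering drug that is neither insulin nor oral.

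- Drug exclusion, both groups: does not catch the person, because it names only insulin and oral agents.
- Unstable medical illness, both groups: does not catch a person whose condition is stable.
- Other exclusions (dementia, neurological disease, substance use, pregnancy or breastfeeding, MRI contraindications and, for controls, psychiatric history): not relevant.
- Analysis, section 6: the drug would be on the baseline medication record and could be used as a covariate or moderator, but nothing commits the analysis to doing so for this class.

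The gap is therefore real. What follows is a sense of scale only.

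**Inputs.** Obese participants: about 25, which is half of 50. This holds only if the subsample described under Neural Circuits Assessment is the whole crossover sample. Group size: 25. Proportion using such a drug, p: not in the documents, so assumed to be 1% to 10%. Shift per user in a metabolic measure: not in the documents, so assumed to be 0.5 to 1 SD.

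**Expected users and chance of at least one among 25.** Expected number = 25 × p; chance = 1 − (1 − p)^25.

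| p | Expected users | Chance of at least one |
|---|---|---|
| 1% | 0.25 | 22% |
| 2% | 0.5 | 40% |
| 5% | 1.25 | 72% |
| 10% | 2.5 | 93% |

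**A related figure from the document.** The background (section 2) puts type 2 diabetes in mood disorders at 8-10%. Among 25 patients that is 25 × 0.08 = 2.0 to 25 × 0.10 = 2.5 cases before exclusions. Only those treated with neither insulin nor an oral agent, but with some other glucose-lowering drug, would pass through the gap. Diabetes prevalence is thus not an estimate of p.

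**Shift in a group mean.** Shift = (users ÷ 25) × shift per user, with all users in one group.

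- One user: 1/25 × 0.5 = 0.02 SD to 1/25 × 1.0 = 0.04 SD.
- Two users: 2/25 × 0.5 = 0.04 SD to 2/25 × 1.0 = 0.08 SD.
- Three users: 3/25 × 0.5 = 0.06 SD to 3/25 × 1.0 = 0.12 SD.

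For comparison, the standard error of an unadjusted difference between two groups of 25 is √(1/25 + 1/25) = 0.28 SD. The range 0.02-0.12 SD is about 7% to 42% of that (0.02/0.283 and 0.12/0.283). Three users is slightly above the largest expected number, 2.5, and users split between the groups would partly cancel, so 0.12 SD is an upper end.

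**The case against.** The case against giving this weight is substantial, and most of it stands.

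- **The numbers are small and assumed.** The documents give no rate of use and no effect on any measure. At 1-2% use, the chance that no user enrols among 25 is 60-78%.
- **Tools for handling it exist.** Current medications are recorded, covariates are open-ended, medications are an example moderator, and the confounder list under Potential Challenges is expressly not exhaustive. What is missing is a commitment for this class. Adjustment that rests on one to three people would also be weak.
- **The plan already accepts drug confounding.** It knowingly admits psychotropic drugs in a naturalistic sample. This does not answer the point, because for glucose-lowering treatment the protocol chose exclusion, and declining to enrol someone withdraws no treatment.
- **The randomized contrast is mostly safe.** Each participant is compared with himself or herself a week apart, so a stable background drug largely cancels, although it could still modify the response to insulin.

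Three stronger readings are tempting and should be resisted. A reader might infer that half of the whole sample must be obese. The text says this of a subsample, section 3 has no BMI criterion, and Potential Challenges speaks of a different category: "we propose to pre-stratify our sample based on overweight/obesity". A reader might also infer that users would cluster in a cell of about 12 obese patients and move its mean by 0.13-0.25 SD. That takes three users in 12, or 25% use, well above the range assumed here, and section 6 plans no comparison of such cells. Finally, a reader might infer from the closing discussion's mention of "the antidiabetic medication liraglutide" that the team knowingly left a drug class out. The passage reports trial experience and does not give that drug's route. The gap does not depend on it.

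**Conclusion.** The criterion is narrower than its stated reason, in both groups, and no other rule closes the gap. This is a minor eligibility-wording defect. It bears on the between-group metabolic comparisons and the mediation models, and does not undermine the insulin-versus-diluent comparison provided use is stable over the week.

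Its likely size is modest: somewhere between no user and a few, and a shift in a group mean of up to about 0.12 SD. That rests on assumed use of 1-10%, an assumed shift of 0.5-1 SD per user, about 25 obese participants, and all users falling in one group. That use would be more common among obese participants is an inference, not something the documents state. The point merits correction because correction is nearly free, and because once someone is enrolled only the analysis can still be changed.

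**What to change.** In both exclusion lists in section 3, align the criterion with its reason by wording it as use of insulin or any other glucose-lowering drug, by any route and for any indication.

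For anyone already enrolled, add to section 6 that users of such drugs are flagged from the baseline medication record, and that the insulin-sensitivity and mediation models are repeated without them as a pre-specified sensitivity analysis. Report the number of users in each group.

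The cost is a few words in two criteria, one sentence in the analytic plan, and the loss of a small number of otherwise eligible people.
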